## **7. SOCIAL IMPACT QUESTIONNAIRE**

Data from the Vaccine Research Center (VRC) Social Impact Questionnaire will be listed and summarized using descriptive statistics.

**APPENDIX 1: LABORATORY, VITAL SIGNS AND ABNORMALITY GRADINGS**

PARAMETER	LABORATORY a			
	GRADE 1 MILD	GRADE 2 MODERATE	GRADE 3 SEVERE	GRADE 4 POTENTIALLY LIFE-THREATENING
HEMATOLOGY				
Absolute Neutrophil Count (ANC) (cells/L) c	800 x 10  – 1.000 x 10 	0.600 x 10  – 0.799 x 10 	0.400 x 10  – 0.599 x 10 	<0.400 x 10 
Hemoglobin (Hgb) (HIV NEGATIVE ONLY)				
Male	10.0 – 10.9 g/dL	9.0 – 9.9 g/dL	7.0 – 8.9 g/dL	<7.0 g/dL
Female	9.5 – 10.4 g/dL	9.4 – 8.5 g/dL	8.4 – 6.5 g/dL	<6.5 g/dL
Platelets, decreased b	100.000 x 10  – 124.999 x 10  /L	50.000 x 10  – 99.999 x 10  /L	25.000 x 10  – 49.999 x 10  /L	<25.000 x 10  /L
WBC, decreased b	2.000 x 10  – 2.500 x 10  /L	1.500 x 10  – 1.999 x 10  /L	1.000 x 10  – 1.499 x 10  /L	<1.000 x 10  /L
CHEMISTRIES				
ALT (SGPT)	1.25 – 2.5 x ULN	2.6 – 5.0 x ULN	5.1 – 10.0 x ULN	>10.0 x ULN
AST (SGOT)	1.25 – 2.5 x ULN	2.6 – 5.0 x ULN	5.1 – 10.0 x ULN	>10.0 x ULN
Creatinine	1.1 – 1.3 x ULN	1.4 – 1.8 x ULN	1.9 – 3.4 x ULN	≥ 3.5 x ULN
URINALYSIS				
Hematuria	6-9 RBC per high power field	≥10 RBC per high power field	Gross, with or without clots or with RBC casts	Transfusion indicated
Proteinuria, random collection	1+	2+	3+ or higher	NA

aThis list is restricted to the laboratory parameters collected in this study for which a DAIDS 2.0 grading is available. Only ranges applicable for adults are reported. For a complete list refer to the CTP appendix 1

bThe decrease is a decrease from baseline

cIf ANC is not available the values will be derived by from the ratio Neutrophils/Leucocytes

VITAL SIGNS a					
PARAMETER	UNIT	GRADE 1	GRADE 2	GRADE 3	GRADE 4
Temperature	°C	≥38.0 - ≤38.5	≥38.6 - ≤39.2	≥39.3 - ≤39.9	≥40.0
Hypertension					
Systolic Blood Pressure	mmHg	≥140 - ≤159	≥160 - ≤179	≥180	NA
Diastolic Blood Pressure	mmHg	≥90 - ≤99	≥100 - ≤109	≥110	NA
Hypotension	mmHg	NA	NA	NA	NA
Pulse rate					
Tachycardia	bpm	≥101-≤115	≥116 - <130	>130	NA
Bradycardia	bpm	≥50 - ≤54	≥45 - ≤49	<45	NA

aDAIDS 2.0 grading, see also CTP appendix 1

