11.5. Safety Analyses

No formal statistical testing of safety data is planned. Safety data will be analyzed descriptively.

Baseline for all safety parameters will be defined as the last evaluation done before the first dose of study vaccine.

AEs

The verbatim terms used in the CRF by investigators to identify AEs will be coded using the Medical Dictionary for Regulatory Activities (MedDRA). All reported AEs and events-related diary information (solicited local at injection site and systemic, and unsolicited) with onset within 28 days after each vaccination (ie, treatment-emergent AEs, and AEs that have worsened since baseline) will be included in the analysis. For each AE, the number and percentage of subjects who experience at least one occurrence of the given event will be summarized by group and/or by vaccine.

Summaries, listings, datasets, or subject narratives may be provided, as appropriate, for those subjects who die, who discontinue treatment due to an AE, or who experience a severe AE, an SAE, or an AESI.

Summaries and listings may be provided separately for AEs with onset outside the above defined timeframe and that were reported pre-dose at the moment of subsequent vaccinations.

Solicited local (at injection site) and systemic AEs will be summarized descriptively. The overall frequencies per vaccine group as well as frequencies according to severity and duration will be calculated for solicited AEs. In addition, the number and percentages of subjects with at least one solicited local (at injection site) or systemic AE will be presented. Frequencies of solicited and unsolicited AEs, separately for all and vaccination-related only, will be presented by System Organ Class and preferred term.

Clinical Laboratory Tests

Laboratory data will be summarized by type of laboratory test. Laboratory abnormalities will be determined according to a modified version of the DAIDS grading table, Version 2.0 ([Attachment 1](#)), and in accordance with the normal ranges of the clinical laboratory. Laboratory abnormalities will be tabulated per treatment group and/or per vaccine.

Vital Signs

The percentage of subjects with values beyond pre-specified limits (see [Attachment 1](#)) will be summarized.

Physical Examination

Physical examination findings will not be tabulated separately. Clinically relevant findings will be reported as AE and will be tabulated and listed as AEs. BMI will be calculated using the recording of height at screening.

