Phosphate, Low (mg/dL; mmol/L) >14 years of age 1 to 14 years of age <1 year of age	2.0 to < LLN 0.81 to < LLN 3.0 to <3.5 0.97 to <1.13 3.5 to <4.5 1.13 to <1.45	1.4 to <2.0 0.65 to <0.81 2.5 to <3.0 0.81 to <0.97 2.5 to <3.5 0.81 to <1.13	1.0 to <1.4 0.32 to <0.65 1.5 to <2.5 0.48 to <0.81 1.5 to <2.5 0.48 to <0.81	<1.0 <0.32 <1.5 <0.48 <1.5 <0.48
Potassium, High (mEq/L; mmol/L)	5.6 to <6.0 5.6 to <6.0	6.0 to <6.5 6.0 to <6.5	6.5 to <7.0 6.5 to <7.0	≥7.0 ≥7.0
Potassium, Low (mEq/L; mmol/L)	3.0 to <3.4 3.0 to <3.4	2.5 to <3.0 2.5 to <3.0	2.0 to <2.5 2.0 to <2.5	<2.0 <2.0

¹⁵ Use the applicable formula (ie, Cockcroft Gault in mL/min or Schwartz in mL/min/1.73m²).¹⁶ To convert a magnesium value from mg/dL to mmol/L, laboratories should multiply by 0.4114.

PARAMETER	GRADE 1 MILD	GRADE 2 MODERATE	GRADE 3 SEVERE	GRADE 4 POTENTIALLY LIFE- THREATENING
Sodium, High (mEq/L; mmol/L)	146 to <150 146 to <150	150 to <154 150 to <154	154 to <160 154 to <160	≥160 ≥160
Sodium, Low (mEq/L; mmol/L)	130 to <135 130 to <135	125 to <130 125 to <135	121 to <125 121 to <125	≤120 ≤120
Uric Acid, High (mg/dL; mmol/L)	7.5 to <10.0 0.45 to <0.59	10.0 to <12.0 0.59 to <0.71	12.0 to <15.0 0.71 to <0.89	≥15.0 ≥0.89

HEMATOLOGY				
PARAMETER	GRADE 1 MILD	GRADE 2 MODERATE	GRADE 3 SEVERE	GRADE 4 POTENTIALLY LIFE- THREATENING
Absolute CD4+ Count, Low (cell/mm³; cells/L) >5 years of age (not HIV infected)	300 to <400 300 to <400	200 to <300 200 to <300	100 to <200 100 to <200	<100 <100
Absolute Lymphocyte Count, Low (cell/mm³; cells/L) >5 years of age (not HIV infected)	600 to <650 0.600×10^9 to <0.650 $\times 10^9$	500 to <600 0.500×10^9 to <0.600 $\times 10^9$	350 to <500 0.350×10^9 to <0.500 $\times 10^9$	<350 $<0.350 \times 10^9$
Absolute Neutrophil Count (ANC), Low (cells/mm³; cells/L) ≥7 days of age 2 to 7 days of age ≤1 day of age	800 to 1,000 0.800×10^9 to 1.000 $\times 10^9$ 1,250 to 1,500 1.250×10^9 to 1.500 $\times 10^9$ 4,000 to 5,000 4.000×10^9 to 5,000 $\times 10^9$	600 to 799 0.600×10^9 to 0.799 $\times 10^9$ 1,000 to 1,249 1.000×10^9 to 1.249 $\times 10^9$ 3,000 to 3,999 3.000×10^9 to 3.999 $\times 10^9$	400 to 599 0.400×10^9 to 0.599 $\times 10^9$ 750 to 999 0.750×10^9 to 0.999 $\times 10^9$ 1,500 to 2,999 1.500×10^9 to 2.999 $\times 10^9$	<400 $<0.400 \times 10^9$ <750 $<0.750 \times 10^9$ <1,500 $<1.500 \times 10^9$

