Fibrinogen, Decreased (mg/dL; g/L)	100 to <200 1.00 to <2.00 OR 0.75 to <1.00 x LLN	75 to <100 0.75 to <1.00 OR ≥0.50 to <0.75 x LLN	50 to <75 0.50 to <0.75 OR 0.25 to <0.50 x LLN	<50 <0.50 OR $<0.25 \times LLN$ OR Associated with gross bleeding
Hemoglobin¹⁷, Low (g/dL; mmol/L)¹⁸ ≥13 years of age (male only) ≥13 years of age (female only) 57 days of age to <13 years of age (male and female) 36 to 56 days of age (male and female) 22 to 35 days of age (male and female) 8 to ≤21 days of age (male and female) ≤7 days of age (male and female)	10.0 to 10.9 6.19 to 6.76 9.5 to 10.4 5.88 to 6.48 9.5 to 10.4 5.88 to 6.48 8.5 to 9.6 5.26 to 5.99 9.5 to 11.0 5.88 to 6.86 11.0 to 13.0 6.81 to 8.10 13.0 to 14.0 8.05 to 8.72	9.0 to <10.0 5.57 to <6.19 8.5 to <9.5 5.25 to <5.88 8.5 to <9.5 5.25 to <5.88 7.0 to <8.5 4.32 to <5.26 8.0 to <9.5 4.94 to <5.88 9.0 to <11.0 5.57 to <6.81 10.0 to <13.0 6.19 to <8.05	7.0 to <9.0 4.34 to <5.57 6.5 to <8.5 4.03 to <5.25 6.5 to <8.5 4.03 to <5.25 6.0 to <7.0 3.72 to <4.32 6.7 to <8.0 4.15 to <4.94 8.0 to <9.0 4.96 to <5.57 9.0 to <10.0 5.59 to <6.19	<7.0 <4.34 <6.5 <4.03 <6.5 <4.03 <6.0 <3.72 <6.7 <4.15 <8.0 <4.96 <9.0 <5.59
INR, High (not on anticoagulation therapy)	1.1 to <1.5 x ULN	1.5 to <2.0 x ULN	2.0 to <3.0 x ULN	≥3.0 x ULN
Methemoglobin (%) hemoglobin)	5.0 to <10.0%	10.0 to <15.0%	15.0 to <20.0%	≥20.0%

¹⁷ Male and female sex are defined as sex at birth.¹⁸ The conversion factor used to convert g/dL to mmol/L is 0.6206 and is the most commonly used conversion factor. For grading hemoglobin results obtained by an analytic method with a conversion factor other than 0.6206, the result must be converted to g/dL using the appropriate conversion factor for the particular laboratory.

PARAMETER	GRADE 1 MILD	GRADE 2 MODERATE	GRADE 3 SEVERE	GRADE 4 POTENTIALLY LIFE- THREATENING
PTT, High (not on anticoagulation therapy)	1.1 to <1.66 x ULN	1.66 to <2.33 x ULN	2.33 to <3.00 x ULN	≥3.00 x ULN
Platelets, Decreased (cells/mm ³ ; cells/L)	100,000 to <124,999 100.000×10^9 to <124,999 $\times 10^9$	50,000 to <100,000 50.000×10^9 to <100,000 $\times 10^9$	25,000 to <50,000 25.000×10^9 to <50,000 $\times 10^9$	<25,000 $<25.000 \times 10^9$
PT, High (not on anticoagulation therapy)	1.1 to <1.25 x ULN	1.25 to <1.50 x ULN	1.50 to <3.00 x ULN	≥3.00 x ULN
WBC, Decreased (cells/mm ³ ; cells/L)				

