## 5.2. Clinical Laboratory Tests

Any clinically relevant lab value measured from signing of the ICF onwards must be recorded on the adverse event page of the CRF and are analyzed as AE. The data will be summarized by the type of laboratory test.

In case a laboratory test result is *censored* (no numeric value is available, but only a verbatim term) then a numeric value will be imputed by a value preceding or exceeding the cut-off value with one unit. (<x: subtract 1 unit from x, >x: add 1 unit to x)

*Toxicity grades* will be determined according to the DAIDS Grading list (see also [APPENDIX 1](#)). In case no toxicity grades are defined for a test, the abnormalities (above/below normal range) will be used. In determining toxicity grades, the following rules are applied:

- worst grades/abnormalities are determined over the whole observational period for each trial phase separately, including all post-baseline measurements of that phase.
- The abnormalities ‘abnormally low’ and ‘abnormally high’ are considered equally important, i.e. if a subject has as well an abnormally low as an abnormally high value post-baseline, both abnormalities are shown in the tables. (This means that the sum of the percentages can be more than 100%)
- Note: as the grading scale for some parameters in the grading table has some gaps (zones where no toxicity grade definition exists), laboratory results falling in these zones will be allocated to the adjacent worst-case grade.
- If a lab value falls within the grading as specified in the grading table but also within the (local) lab normal limits, the value is considered as normal

Definition emergent: An abnormality (toxicity grade or abnormality based on normal ranges) will be considered emergent in a particular phase if it is worse than the baseline (baseline = prior very first vaccination). If the baseline is missing, the abnormality is always considered as emergent. A shift from ‘abnormally low’ at baseline to ‘abnormally high’ post baseline (or vice versa) is also emergent.

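### SAP Appendix 1 contradicts protocol Attachment 1 on platelet, WBC and ANC grading, and would misgrade these tests if programmed as written

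*SAP*

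**What the plan says.** Protocol 11.5 fixes the grading source: "Laboratory abnormalities will be determined according to a modified version of the DAIDS grading table, Version 2.0", that is, Attachment 1. In the haematology part of Attachment 1, the row "Platelets, Decreased" has a Grade 1 band of "100,000 to <124,999" cells/mm³ and a Grade 4 band below 25,000. WBC runs from 2,000–2,499 (Grade 1) to below 1,000 (Grade 4). The row "Absolute Neutrophil Count (ANC), Low" has Grade 1 at 800 to 1,000 cells/mm³. None of these rows refers to baseline.

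SAP Appendix 1 restates the ranges per litre. Its rows "Platelets, decreased" and "WBC, decreased" carry essentially the same absolute bands, but both are marked with footnote b: "The decrease is a decrease from baseline". Its ANC Grade 1 cell runs from 800 × 10⁹ to 1.000 × 10⁹ cells/L.

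SAP 5.2 says that toxicity grades follow the DAIDS list and refers the reader also to Appendix 1. For values in zones with no grade definition it adds: "laboratory results falling in these zones will be allocated to the adjacent worst-case grade". A value inside the local normal limits counts as normal. Baseline enters SAP 5.2 only through the definition of an emergent abnormality, which is one worse than baseline.

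**The concern.** A programmer has two sources for the same grades, with different content and no stated precedence. For platelets and WBC, the bands describe a count while the footnote describes a change. On an absolute scale a lower number is worse. On a scale of falls a lower number is better. Applying these bands to the fall therefore reverses their meaning: a small fall lands in Grade 4, and a fall larger than the top of Grade 1 lands in no band.

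The ANC cell is a separate fault. Its lower limit exceeds its upper limit, so read literally no value is Grade 1.

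SAP 5.2.1 uses these grades for the tables of worst grade by post-vaccination period and for the listing of Grade 3 and 4 toxicities. In a study that is first-in-human for the tetravalent vaccine, these are the main summaries of laboratory toxicity.

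**Working it through.** **Inputs.** The bands come from SAP Appendix 1 and protocol Attachment 1. Eligible baselines come from protocol 4.1: platelets 125–450 and WBC 2.5–11.0. All counts below are × 10⁹/L. The conversion is cells/mm³ × 10⁶ = cells/L, so 1,000 cells/mm³ = 1.000 × 10⁹/L.

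**Step 1: do the bands agree after conversion?**
- Platelets: 124,999, 100,000, 50,000 and 25,000/mm³ become 124.999, 100, 50 and 25. These match the SAP.
- WBC: 2,499, 2,000, 1,500 and 1,000/mm³ become 2.499, 2.0, 1.5 and 1.0. These match, except that the SAP closes Grade 1 at 2.500.
- ANC: 800–1,000/mm³ becomes 0.800–1.000. The SAP upper limit matches. The lower limit does not: 800 / 0.800 = 1000. SAP Grades 2 to 4 (0.600–0.799, 0.400–0.599, below 0.400) match.

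**Step 2: platelets and WBC under the two readings.** The literal reading of footnote b applies the bands to fall = baseline − post-dose value.

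| Test | Baseline → post-dose | Attachment 1 (count) | Fall | Bands applied to the fall |
|---|---|---|---|---|
| Platelets | 250 → 20 | Grade 4 | 230 | none (above 124.999) |
| Platelets | 160 → 120 | Grade 1 | 40 | Grade 3 |
| WBC | 6.0 → 1.4 | Grade 3 | 4.6 | none (above 2.500) |
| WBC | 3.2 → 2.4 | Grade 1 | 0.8 | Grade 4 |

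The second and fourth rows assume that the post-dose value is below the local normal limit, which the documents do not give. Otherwise the normal-range rule in SAP 5.2 removes the false grade.

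**Step 3: how much of the eligible range is exposed?** Under the literal reading, every count in a grade goes ungraded once baseline reaches the top of the Grade 1 band plus the top of that grade's band.
- Platelets, any grade: 125 + 125 = 250. Grade 3: 125 + 50 = 175. Grade 4: 125 + 25 = 150.
- WBC, any grade: 2.5 + 2.5 = 5.0. Grade 3: 2.5 + 1.5 = 4.0. Grade 4: 2.5 + 1.0 = 3.5.

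These thresholds lie low in the eligible ranges of 125–450 and 2.5–11.0.

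**Step 4: do the SAP 5.2 rules repair this?** The gap rule concerns undefined zones in the scale. A fall past the mild end of the scale is not clearly such a zone, and if it were treated as one, the neighbouring band is Grade 1, not Grade 4. The normal-range rule can cancel false grades but cannot restore a missed one.

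**Step 5: ANC.** An ANC of 0.90 is Grade 1 in Attachment 1. With the Grade 1 cell empty it falls in an undefined zone, and the gap rule sends it to Grade 2. The error is one grade upward. No low ANC is left ungraded, and Grades 3 and 4 do not change.

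**The case against.** The strongest reply is that nobody would program footnote b literally. SAP 5.2 names the DAIDS list first and Appendix 1 only as a further reference, and Appendix 1 itself points to the protocol for the complete list. The normal-range rule compares the laboratory value, not a difference, with the bands. A scale on which smaller falls are worse is absurd on its face. The footnote may simply mean lower than baseline, in which case no grade changes. The intended ANC limit is also plain from Grade 2 ending at 0.799, and a 0. lost when the PDF text was read cannot be excluded.

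Much of this stands. It makes literal programming less likely, but it does not remove the contradiction. On the benign reading the footnote is redundant, because the emergent definition already covers worsening from baseline. Deleting it is right either way.

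A reader might infer that haematological toxicity in this trial was in fact misgraded and severe cytopenia missed. The documents do not support that, because they do not show how grading was programmed. Nor does the problem cover all haematology: the haemoglobin bands are sound. Pause decisions are not affected either. The holding rules in protocol 11.9 work from events reported by sites, and protocol 9.3 and 12.1.3 grade these under Attachment 1. Clinically relevant laboratory values are also reported as adverse events, which gives a second route by which a true cytopenia would appear.

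It is also fair that little prospective grading remains. The SAP Introduction says that the Week 72 analysis is complete and will not be repeated, and the extension-phase schedule has no blood count.

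**Conclusion.** The contradiction is real and should be corrected. Appendix 1 departs from Attachment 1 in two places: a footnote that turns absolute platelet and WBC bands into changes from baseline, and an ANC Grade 1 lower limit printed 1000-fold too high.

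The consequence is conditional. If the appendix was programmed as written, the worst-grade tables could be wrong for all three tests, and the Grade 3/4 listing could be wrong for platelets and WBC. True Grade 3 or 4 counts could go ungraded over most of the eligible baseline range, and some mild decreases could appear as Grade 3 or 4 if they lie below local normal limits. For ANC, the effect is limited to over-grading by one step between 0.80 and 1.00 × 10⁹/L.

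The conclusion that there is a conflict rests only on the printed tables. Whether any output is wrong depends on the Week 72 program and on the SAP version it followed, neither of which the documents show.

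**What to change.** 1. Delete footnote b, so that platelets and WBC are graded on the absolute post-baseline count as in Attachment 1. The emergent definition in SAP 5.2 already handles worsening from baseline.
2. Correct ANC Grade 1 to 0.800–1.000 × 10⁹/L, after checking the source file in case the printed limit is a text-reading loss.
3. Confirm that the completed Week 72 grading program used the Attachment 1 absolute counts for all three tests, and record the result.
4. Only if it did not, re-issue the affected worst-grade tables and Grade 3/4 listing. This would be a stated exception to the SAP Introduction, which says that Week 72 will not be rerun.

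The cost is two edits to an appendix and a program check. No new data are needed. A re-run of the laboratory grading is needed only if the check fails.
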